12-lead ECG	7.4.7 Table 7	X	X (Pre, EOI, Post) ⁹				C3, C5 and every other Cycle (Pre) ⁹		X	
Camidanlumab tesirine premedication	6.9.1		D-1 to D2				D-1 to D2 ¹⁰			
Camidanlumab tesirine Administration	6.4		X				X, starting Cycle 5 ¹¹			
Pembrolizumab administration	6.4		X ¹²				X			
PK sample ¹³	7.5.1 Table 9		X (Pre, EOI, Post)	X	X	X	C3, C4, C5, C6, C7 then every other cycle (Pre)		X	
ADA sample ¹⁴	7.5.2 Table 9		X (Pre)			X C1 only	C3, C4, C5, C6, C7 then every other cycle (Pre)		X ¹⁵	X ¹⁵
Additional microbiological studies	7.4.5		In case of suspicion of infection and GBS							
Concomitant medications	6.10		From ICF signature date or D-14, whichever is earlier, until 30 days after last dose of study treatment							
Adverse events	8		AE/SAEs from ICF signature date until 30 days after last dose of study treatment; thereafter, related SAEs only							

	Protocol Section	Screening	Treatment Period							Follow-up Period up to 1 year from EOT	
			Cycle 1 and Cycle 2 (C1 and C2)				C3 and beyond				
(1 cycle = 21 days)											
Day (D)		-21 to -1	1	3 and 5	8	15		1	8¹		
1 st New anticancer treatment	4.2.3									X	X
Survival	4.2.4									X	X

Abbreviations: ADA=anti-drug antibody; (S)AE=serious adverse event; BP=blood pressure; [REDACTED]; [REDACTED]; D=day; DESC=dose-escalation meeting committee; ECG=electrocardiogram; ECOG=Eastern Cooperative Oncology Group; EOI=end of infusion; EOT=end of treatment; GBS=Guillain-Barré syndrome, [REDACTED]; HR=heart rate; ICF=informed consent form; MMR=mismatch repair; MSI=microsatellite instability; MSS=microsatellite stability; PK=pharmacokinetic; RR=respiratory rate; SAE=serious adverse event; SARS-CoV-2=severe acute respiratory syndrome coronavirus; Temp=temperature; VZV=varicella zoster virus; wk=week.

- ¹ After completion of Cycle 4, the Day 8 visit is not required unless clinically indicated.
- ² Timing of biopsy may be adjusted based on emerging evidence. The on-treatment biopsy should be performed between Cycle 2 Day 8 and Cycle 2 Day 15, before the disease assessment. For patients with sufficient available archival tumor tissue prior to C1D1 (biopsied after their last disease progression, and in the situation where the patient has received no anti-cancer therapy between their progression and C1D1), a fresh biopsy prior to C1D1 may not be needed. This archived tissue will be used in lieu of the fresh biopsy and the screening window will not apply to this sample obtained routinely prior to ICF signature.
- ³ In Dose-escalation, for patients with NSCLC or melanoma, PD-L1 expression is requested; MMR/MSS/MSI status is not required. In Dose-escalation, for patients with colorectal cancer, gastric-esophageal cancer, ovarian/fallopian tube cancer, pancreatic cancers: if MMR/MSS/MSI status is not available at signature of the informed consent, the test should be performed before C1D1. In Dose-expansion, for patients enrolled in Group 1, if MMR/MSS/MSI status is not available at signature of the informed consent, the test should be performed before C1D1. In Dose-expansion, for patients enrolled in Group 2, MSI-H/dMMR status must be available prior to ICF signature.
- ⁴ Imaging performed within 4 weeks prior to C1D1 (beyond the screening period) can be accepted as the Screening (Baseline) assessment, and the same assessment method should be used throughout the study. During the treatment period, imaging will be performed 6 weeks (42 days \pm 7 days) after C1D1, but prior to C3D1, and 12 weeks (84 days \pm 7 days) after C1D1, but prior to C5D1, then every 9 weeks (63 days \pm 14 days) until EOT. During the follow-up period, patients who discontinued study drug for reasons other than disease progression or initiation of other anti-cancer therapy will have imaging performed every 9 weeks (63 days \pm 14 days) until 1 year from EOT. Disease assessments should be performed at the timepoints specified even if study drug dosing is delayed. If a scan has been performed within 8 weeks of EOT, it does not need to be repeated at EOT. Confirmation of progression should be performed as per iRECIST, i.e., 4 to 8 weeks after the first progressive disease assessment; if progression is not confirmed, disease assessment should continue as originally planned.
- ⁵ Disease assessments to be performed in patients having discontinued study treatment for reasons other than disease progression or initiation of other anti-cancer therapy.
- ⁶ Vital signs will be done pre-dose, at end of infusion of camidanlumab tesirine and at end of infusion of pembrolizumab.

- 7 Serology testing for human immunodeficiency virus, hepatitis B virus, or hepatitis C virus is mandatory at screening for patients with unknown status. Seropositive patients for or with prior history of these infections at screening will be tested during the study (not needed if seropositivity is only due to vaccination).
- 8 A pregnancy test should be performed ≥ 9.5 months after the last dose of camidanlumab tesirine or ≥ 4 months after last dose of pembrolizumab, whichever is the latest.
- 9 Pre-dose is preferably within 2 hours prior to the start of infusion of camidanlumab tesirine. EOI is within 10 minutes prior to the end of infusion of camidanlumab tesirine. Post-dose is 4 hours from the start of infusion of camidanlumab tesirine.
- 10 Only when camidanlumab tesirine is administered.
- 11 Additional administration of camidanlumab tesirine is allowed for patients who tolerate the combination and are in disease control after the first tumor assessment. Additional camidanlumab tesirine administration concomitantly to pembrolizumab would be given as follow: 2 consecutive Cycles every 2 Cycles, starting from Cycle 5 up to a year (i.e., Cycle 5 and 6, Cycle 9 and 10, Cycle 13 and 14, Cycle 17 and 18) if there is no delay in the planned treatment schedule, or, in case of delay in the administration of pembrolizumab, after respecting a minimum of 63 days (9 weeks) between the last dose of camidanlumab tesirine and the first dose of the 2 subsequent additional administrations of camidanlumab tesirine. Between these cycles, patients should receive pembrolizumab as a single agent.
- 12 Alternative Schedules may be investigated based on observed safety and efficacy data, as assessed by the DESC: pembrolizumab from Cycle 2 onwards (Schedule 2). When administered on the same day, camidanlumab tesirine is to be administered prior to pembrolizumab separated by 1 hour (or more if clinically indicated).
- 13 Pre-dose is preferably 2 hours prior to the start of infusion of camidanlumab tesirine or 2 hours prior to the start infusion of pembrolizumab, in visits without camidanlumab tesirine administration. EOI is to be done within a window of 5 minutes prior to EOI to 10 minutes after EOI. Post-dose is 4 hours from the start of infusion of camidanlumab tesirine. Collection of PK is stopped if camidanlumab tesirine administration is discontinued.
- 14 Pre-dose is within 2 hours prior to the start of infusion of camidanlumab tesirine or 2 hours prior to the start infusion of pembrolizumab, in visits without camidanlumab tesirine administration. Collection of ADA is stopped if camidanlumab tesirine administration is discontinued.
- 15 Patients who test positive for ADAs will be requested to supply additional ADA samples.
- [REDACTED]
- [REDACTED]

Visit Scheduling Windows:

- Treatment Period: C1D1 is the reference day, D3 and D5: visit day ± 1 day (combined D3 and D5 visit is not allowed), otherwise visit day ± 2 days
- EOT: as soon as possible after decision to discontinue the study treatment, preferably within 30 days after last dose of study treatment, and before initiation of any new anticancer treatment
- Follow-up Period: visit day ± 14 days

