¹ After completion of 4 treatment cycles, the Day 8 visit is not required unless clinically indicated.

² Timing of on-treatment biopsy and other [REDACTED] sample(s) may be adjusted based on emerging evidence.

³ Imaging performed within 4 weeks prior to C1D1 (beyond the screening period) can be accepted as the Screening (Baseline) assessment, and the same assessment method should be used throughout the study. Week 6 imaging should be performed within 1 week prior to C3D1 and Week 12 imaging should be performed within 1 week prior to C5D1.

All other imaging for disease assessment for patients on study drug should be performed within ± 2 weeks of the scheduled timepoint. Disease assessments should be performed at the timepoints specified even if study drug dosing is delayed. If a scan has been performed within 8 weeks of EOT, it does not need to be repeated at EOT. Confirmation of progression should be performed as per iRECIST, i.e., 4 to 8 weeks after the first progressive disease assessment; if progression is not confirmed, disease assessment should continue as originally planned.

⁴ Disease assessments to be performed in patients having discontinued study drug for reasons other than disease progression or initiation of other anti-cancer therapy.

⁵ Vital signs to be measured pre, during (only BP and heart rate), and at EOI. During infusion, BP and HR will be measured every 30 minutes.

⁶ Serology testing for human immunodeficiency virus, hepatitis B virus, or hepatitis C virus is mandatory at screening for patients with unknown status. Seropositive patients for or with prior history of these infections at screening will be tested during the study (not needed if seropositivity is only due to vaccination).

⁷ A pregnancy test should be performed ≥ 6.5 months after the last dose of camidanlumab tesirine.

⁸ Pre-dose is preferably 2 hours prior to start of infusion of camidanlumab tesirine during Cycle 1 Day 1, and within 30 minutes prior to PK sample for Cycle 2 Day 1. EOI is to be done within 10 minutes prior to EOI. Post-dose is 4 hours from the start of infusion of camidanlumab tesirine.

⁹ Pre-dose is within 30 minutes prior to PK sample. Post-dose is 4 hours from the start of infusion of camidanlumab tesirine.

¹⁰ Pre-dose is preferably 2 hours prior to start of infusion of camidanlumab tesirine. EOI is to be done within 5 to 10 minutes prior to EOI. Post-dose is 4 hours from the start of infusion of camidanlumab tesirine.

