1.3.4 ADCT-301-103

As of 14 April 2021, enrolment in the monotherapy part was completed; 44 patients were treated with camidanlumab tesirine monotherapy in Part 1 at 8 dose levels ranging from 20 to 150 $\mu\text{g}/\text{kg}$ administered on a 3-week treatment cycle and the MTD has not been reached.

The most frequently reported TEAEs ($\geq 20\%$ overall), regardless of grade or relationship, included: nausea (40.9%), fatigue and decreased appetite (36.4% each), constipation (29.5%), abdominal pain (27.3%), rash (22.7%). ([Puzanov, 2021](#)).

The TEAEs that have been assessed as Grade ≥ 3 were reported in 31 out of 44 (70.5%) patients. The most common Grade ≥ 3 TEAEs (observed in at least 5% of patients overall), regardless of relationship, included anemia (11.4%), abdominal pain, rash and pulmonary embolism (6.8% each).

Grade 3 autoimmune AE (colitis, immune-mediated adverse event, systemic inflammatory response syndrome) and grade 3 neurologic AE (dysphagia and asthenia), regardless of relationship, were observed in 6.8% and 4.5% of the patients, respectively.

Best overall responses were stable disease (SD) for 11 patients (25%) and progressive disease (PD) for 23 patients (52.3%); 2 patients were not evaluable (4.4%) and 8 (18.2%) had no post-baseline evaluation due to death (11.4%) or clinical progression (6.8%).

Some patients with paired biopsies showed decreased Tregs and increased Teffs:Tregs ratio in the local tumor environment, supporting a therapeutic rationale for the treatment of advanced solid tumors with camidanlumab tesirine in combination with other immune-modulating therapies ([Puzanov, 2020](#)).

At the time of this Protocol Amendment 7, the study is enrolling patients receiving camidanlumab tesirine in combination with pembrolizumab.

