4.2.2 Treatment Period

The treatment period starts on the date when a patient receives the first dose of study drug and continues until end of treatment visit.

A treatment cycle is defined as 3 weeks (i.e., 21 days).

After completion of Cycle 4, the Day 8 visit is not required unless clinically indicated.

Patients may continue treatment for up to 1 year or until disease progression, unacceptable toxicity, or other discontinuation criteria (Section 5.4), whichever occurs first. Additionally, patients benefiting clinically at 1 year may continue treatment after a case by case review with the Sponsor.

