 - e. Total bilirubin $\leq 1.5 \times$ ULN (patients with known Gilbert's syndrome may have a total bilirubin up to $\leq 3 \times$ ULN with direct bilirubin $\leq 1.5 \times$ ULN).
 - f. Blood creatinine $\leq 1.5 \times$ ULN or calculated creatinine clearance (CL) $\geq 60 \text{ mL/min}$ by the Cockcroft-Gault equation.

Note: A laboratory assessment may be repeated a maximum of two times during the Screening period to confirm eligibility.

10. Negative beta-human chorionic gonadotropin (β -HCG) pregnancy test within 7 days prior to start of study drug (C1D1) for women of childbearing potential (WOCBP).

11. Women of childbearing potential* must agree to use a highly effective** method of contraception from the time of giving informed consent until at least 9.5 months after the last dose of camidanlumab tesirine or 4 months after last dose of pembrolizumab, whichever is the latest. Men with female partners who are of childbearing potential must agree to use a condom when sexually active or practice total abstinence from the time of giving informed consent until at least 6.5 months after the patient receives his last dose of camidanlumab tesirine or 4 months after last dose of pembrolizumab, whichever is the latest.

* Women of childbearing potential are defined as sexually mature women who have not undergone bilateral tubal ligation, bilateral oophorectomy, or hysterectomy; or who have not been postmenopausal (i.e., who have not menstruated at all) for at least 1 year.

** Highly effective forms of birth control are methods that achieve a failure rate of less than 1% per year when used consistently and correctly. Highly effective forms of birth control include: hormonal contraceptives associated with inhibition of ovulation (oral, injectable, patch and intrauterine devices), male partner sterilization, or total abstinence from heterosexual intercourse, when this is the preferred and usual lifestyle of the patient.

Note: The double-barrier method (e.g., synthetic condoms, diaphragm, or cervical cap with spermicidal foam, cream, or gel), periodic abstinence (such as calendar, symptothermal, post-ovulation), withdrawal (coitus interruptus), lactational amenorrhea method, and spermicide-only are not acceptable as highly effective methods of contraception.

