7.4.6 Pregnancy Test

A highly sensitive β -HCG test in urine or blood β -HCG test will be performed in WOCBP for eligibility (see Section 5.1) and throughout the study as per SoE.

The C1D1 pre-dose pregnancy test can be waived if the test for eligibility was done within 7 days of C1D1. After starting the study drug, all efforts should be made to keep the interval between two consecutive pregnancy tests no more than 6 weeks.

If a pregnancy test is positive, the study drug must be held pending confirmation. If the pregnancy is confirmed, study treatment will be discontinued permanently for the patient. Refer to Section 8.6 for the handling of the patient and reporting the event.

A pregnancy test is to be performed at the EOT visit. In addition, a pregnancy test should be performed ≥ 9.5 months after the last dose of camidanlumab tesirine (i.e., end of relevant systemic exposure considering 5 half-lives plus 6 months for other than aneugenic genotoxic compound [CTFG, 2020; FDA, 2019] or ≥ 4 months after the last dose of pembrolizumab, whichever is the latest. The patient will be asked either to come back to the site for a pregnancy test or she will be given a prescription for a pregnancy test. The result will be collected over the phone or will be faxed/mailed to the site. The contact with the patient and the result of the pregnancy test must be documented on source documents at the site.

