8.6 Pregnancy Reporting

Any pregnancy in a participant that occurs from signing the ICF up to 9.5 months after the last dose of camidanlumab tesirine, or up to 4 months after the last dose of pembrolizumab, whichever is the latest, must be reported using the Pregnancy Report Form. Any pregnancy in a partner of a male patient that occurs from signing the ICF up to 6.5 months after the last dose of camidanlumab tesirine, or up to 4 months after the last dose of pembrolizumab, whichever is the latest, must be reported. Pregnancy must be reported within 24 hours after the site personnel first learn of the pregnancy. The pregnancy itself is not considered an AE. However, the pregnancy must be followed to determine outcome (including spontaneous

miscarriage, elective termination, normal birth, or congenital abnormality) and status of mother and child, even if the patient discontinued from the study. Abortions (elective or spontaneous) must be reported as an SAE.

Any SAE occurring in association with a pregnancy that is brought to the Investigator's attention after the patient has completed the study and considered by the Investigator as possibly related to the study drug must be promptly reported in the same manner.

Once pregnancy is confirmed in a study participant, study drug will be discontinued; see Section [7.4.6](#) for additional information.

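### The monotherapy schedule (Table 1, footnote 7) allows the post-treatment pregnancy test from 6.5 months after the last dose, but Section 7.4.6 sets at least 9.5 months

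*Protocol*

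**What the plan says.** Two parts of the current protocol give different earliest times for the same test in the same women.

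- **Table 1 (monotherapy), footnote 7:** "A pregnancy test should be performed ≥ 6.5 months after the last dose of camidanlumab tesirine".
- **Section 7.4.6:** "a pregnancy test should be performed ≥ 9.5 months after the last dose of camidanlumab tesirine", or 4 months after the last pembrolizumab dose if that is later. The section is not restricted by treatment. It bases the camidanlumab tesirine figure on five half-lives plus 6 months.

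The pregnancy-test row of Table 1 names Section 7.4.6 as its governing section. Three other places use 9.5 months for women:

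- **Table 2 (combination), footnote 8:** "A pregnancy test should be performed ≥ 9.5 months after the last dose of camidanlumab tesirine".
- **Section 5.1, criterion 11 (contraception):** "until at least 9.5 months after the last dose of camidanlumab tesirine".
- **Section 8.6 (reporting of pregnancies in participants):** "from signing the ICF up to 9.5 months after the last dose of camidanlumab tesirine".

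Apart from footnote 7, 6.5 months appears only for men. It is the condom or abstinence period in criterion 11 and the reporting period in Section 8.6 for a pregnancy in the "partner of a male patient that occurs from signing the ICF up to 6.5 months after the last dose of camidanlumab tesirine".

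**The concern.** Both figures are operative text, so this is not merely a difference from an amendment log. Footnote 7 permits a test between 6.5 and 9.5 months. Section 7.4.6 does not.

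Nothing suggests a deliberate shorter interval for monotherapy. The 9.5 months comes from camidanlumab tesirine alone, and pembrolizumab enters only as a separate 4-month alternative. Removing pembrolizumab therefore cannot shorten the interval.

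At stake is detection of a late pregnancy after exposure to a genotoxic drug. Section 7.4.6 provides for one further test after the end-of-treatment (EOT) visit. If it is done at 6.5 months, the rest of the contraception and reporting period has no scheduled test. Section 8.6 requires a known pregnancy to be reported, but it does not find one. A site that follows its schedule table would also depart from Section 7.4.6 without knowing it.

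**Working it through.** **1. The gap.** Taking 30.4375 days per month:

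- 6.5 months = 6.5 × 30.4375 = 197.8 days
- 9.5 months = 9.5 × 30.4375 = 289.2 days
- Gap = 3.0 months = 91.3 days, and 91.3 / 289.2 = 32% of the required interval

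**2. Can 6.5 months come from the protocol's own rule?** The half-life is not given in the text available, so 9.5 months cannot be reproduced directly. Solving backwards from five half-lives plus 6 months tests consistency only:

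| Total | Add-on | Left for 5 half-lives | Implied half-life |
|---|---|---|---|
| 9.5 months | 6 months | 3.5 months = 106.5 days | 21.3 days |
| 6.5 months | 6 months | 0.5 month = 15.2 days | 3.0 days |
| 6.5 months | 3 months (assumed) | 3.5 months = 106.5 days | 21.3 days |

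One drug cannot have both half-lives under one rule. The men's 6.5 months fits the same exposure as the women's 9.5 months if the add-on for men is 3 months. That add-on is an assumption, not stated in the documents.

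**3. What happens at the follow-up contacts.** Let EOT fall *e* days after the last dose, with *e* from 0 to 30 (Section 4.2.3 prefers within 30 days). Contacts are every 12 weeks from EOT (Section 4.2.4). Assume nominal timing, and the test done at the first contact that meets the floor.

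- *Floor of 6.5 months.* The Week 24 contact falls on day 168 + *e* and reaches day 197.8 only at *e* = 30 (day 198), which is 91 days short of 9.5 months. For *e* = 0 to 29 the first qualifying contact is Week 36, on day 252 + *e* = 252 to 281, which is 37 to 8 days short.
- *Floor of 9.5 months.* The Week 36 contact reaches at most day 252 + 30 = 282, which is too early. The Week 48 contact falls on day 336 + *e* = 336 to 366. That is after day 289 and within 1 year of EOT.

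The ±14-day follow-up window widens the early range. A Week 24 contact held 14 days late falls on day 182 + *e* and meets the 6.5-month floor from *e* = 16. Section 7.4.6 also allows the test by prescription, away from a visit, so it could be done on any day from 6.5 months.

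**4. Who could be affected.** Section 1.3.4 states: "As of 14 April 2021, enrolment in the monotherapy part was completed; 44 patients were treated with camidanlumab tesirine monotherapy in Part 1". Part 2 is combination only, so no new patient falls under Table 1. Section 4.2.2 states: "Patients may continue treatment for up to 1 year or until disease progression", with case-by-case extension beyond 1 year.

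- Latest window under the 1-year cap, taking first dose by 14 April 2021: 14 April 2021 + 1 year = 14 April 2022, and + 289 days = 28 January 2023.
- Earliest reference date: the date of Amendment 8 is not in the text, but it follows Amendment 7 (2 September 2021). 2 September 2021 − 289 days = 17 November 2020. On that date, women last dosed after about 17 November 2020 were still inside the window.

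**The case against.** The best case on the other side accepts the mismatch and argues that it is only editorial.

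- **Few or no women are affected.** Of the 44 monotherapy patients, 23 had progressive disease as best response, 8 had no post-baseline evaluation because of death or clinical progression, 2 were not evaluable and only 11 had stable disease. Long treatment should be uncommon, and so should a window still open after Amendment 8. *This stands.* It limits the harm, but the documents do not show that the number is zero.
- **The main protections are already right.** Contraception and reporting run to 9.5 months, contacts continue every 12 weeks, and the Table 1 row points to Section 7.4.6. *This stands too.* But follow-up contacts may be by phone when no disease assessment is planned, and a reporting duty does not replace a test.
- **A floor of 6.5 months does not forbid a test at 9.5 months.** *True.* A later test meets both texts. The conflict lies in the earlier tests that footnote 7 allows.
- **The full 91 days is an edge case.** With nominal visits and EOT within 29 days, the shortfall is 8 to 37 days. *Fair*, so 91 days should be read as a maximum. Visit windows and tests by prescription can still bring a test close to it.
- **The January 2023 date is soft.** The SAP counts patients as enrolled at consent, and screening can take up to 21 days, so a first dose might fall after 14 April 2021. *Accepted.* This would move the date by at most 21 days, to 18 February 2023.
- **Sites may already know.** The Summary of Changes links the longer contraception period to an urgent safety measure. *Possible*, but the documents do not show what sites were told about this test.

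**Conclusion.** The concern holds. Footnote 7 gives the wrong floor for women on monotherapy by the protocol's own rule. It conflicts with Section 7.4.6 and falls short of the periods in criterion 11 and Section 8.6. Table 2 footnote 8 covers combination patients only, so it supports the reading rather than conflicting directly. The likely explanation is a footnote that was not updated: the Summary of Changes for Amendment 8 names Table 2 among the revised places and does not name Table 1.

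The error is up to 3.0 months (about 91 days), and 8 to 37 days under nominal visits with EOT 0 to 29 days after the last dose. The affected group is closed and may be small or empty. The 28 January 2023 limit assumes first dose by 14 April 2021 and no extension beyond 1 year. No sample size or analysis is affected, because SAP Section 4.9.7 only lists pregnancy tests. It should still be corrected, because this is an operative safety instruction and the correction is trivial.

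**What to change.** Change Table 1 footnote 7 from 6.5 to 9.5 months after the last dose of camidanlumab tesirine.

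Check whether any monotherapy woman of childbearing potential is still within 9.5 months of her last dose. If so, notify her site, and repeat the test at or after 9.5 months if it was done earlier. If there is none, the footnote correction is enough.

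The cost is one number in one footnote and, if needed, a short site notice. No extra contact is required, because the Week 48 contact already falls after 9.5 months and within the 1-year follow-up. The SAP needs no change.
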